2. INTRODUCTION

Guselkumab is a fully human immunoglobulin G1 lambda monoclonal antibody that binds to the p19 protein subunit of human interleukin (IL)-23 with high specificity and affinity. By binding to the p19 subunit of IL-23, guselkumab blocks the binding of extracellular IL-23 to the cell surface IL-23 receptor, inhibiting IL-23 mediated intracellular signaling, activation and cytokine production including IL-17A, IL-17F, and IL-22.

A rapidly growing body of literature suggests that the IL-23 pathway contributes to the chronic inflammation underlying the pathophysiology of many immune-mediated diseases including psoriasis, psoriatic arthritis, ankylosing spondylitis, and inflammatory bowel disease (IBD). Susceptibility to psoriasis, psoriatic arthritis, and IBD has been shown to be associated with genetic polymorphisms in IL-23/IL-23 receptor components.

Guselkumab is currently being studied in participants with Crohn's disease (see details in Section 2.2).

For the most comprehensive nonclinical and clinical information regarding guselkumab, refer to the latest version of the Investigator's Brochure (IB) for guselkumab (IB guselkumab).

The term "study intervention" throughout the protocol, refers to study drug.

The term "sponsor" used throughout this document refers to the entities listed in the Contact Information page(s), which will be provided as a separate document.

The term "participant" throughout the protocol refers to the common term "subject".

2.1. Study Rationale

Crohn's disease is a chronic, progressive and potentially life-threatening disorder which may affect any part of the gastrointestinal (GI) tract. Inflammation penetrates the lining of the GI tract and often causes ulcers to form. Symptoms may include abdominal pain (AP), diarrhea, fatigue, and weight loss/anorexia. Painful perianal disease, strictures, and fistulas are common. Patients with high disease burden often require at least one surgical intervention.

The pathophysiology of IBD is complex and thought to be multifactorial. The primary aim of pharmacotherapy is to control the inflammatory response, thereby relieving symptoms and promoting mucosal healing. The specific goals of IBD management include the treatment of acute exacerbations, prevention of relapses, treatment of specific complications, and surveillance of malignant transformation (D'Haens 2014; Lichtenstein 2018).

Historically, the treatment of Crohn's disease has relied mainly on corticosteroids and immunosuppressive medications such as thiopurines or methotrexate. Although corticosteroids reduce mortality in Crohn's disease patients, corticosteroids are associated with multiple significant adverse effects and therefore are not suitable for long-term treatment. Approximately 2 decades ago, tumor necrosis factor alpha (TNFα) inhibitors such as infliximab, adalimumab, and

certolizumab became available for treatment of patients with moderately to severely active Crohn's disease, especially those who did not respond to corticosteroids, or were refractory or intolerant to conventional immunosuppressive medications (Nielsen 2013). In recent years, other biologics have become available, such as the anti-α4β7-integrin monoclonal antibody (ie, vedolizumab) and the IL-12/23p40 antibody (ie, ustekinumab). Current treatment guidelines recommend the use of TNFα inhibitors, vedolizumab, or ustekinumab based on their efficacy and safety profiles (Lichtenstein 2018; Torres 2020). However, despite the availability of these therapies, many patients experience primary or secondary nonresponse, hence the unmet medical need remains high and underscores the need for novel treatment options that provide greater therapeutic value to patients (Gordon 2015; Sandborn 2016).

Currently, the GALAXI clinical program is evaluating guselkumab intravenous (IV) induction dosing followed by subcutaneous (SC) maintenance dosing in participants with moderately to severely active Crohn's disease who have demonstrated an inadequate response or failure to tolerate previous conventional therapy or biologic therapy. Under the GALAXI protocol, there are 3 separate studies (Phase 2 study GALAXI 1 and Phase 3 studies GALAXI 2 and GALAXI 3). Results from the GALAXI 1 study show that guselkumab IV induction demonstrated greater improvements compared to placebo across the key clinical efficacy and endoscopic outcome measures at Week 12 (Danese 2021; Sandborn 2020b).

In the current study, the sponsor is interested in assessing SC administration of guselkumab for the induction phase of Crohn's disease treatment. Subcutaneous delivery of biologic agents has become a valuable alternative to IV administration across many disease areas (De Cock 2016; Gardulf 2007; Tetteh 2014; Usmani 2021). Although the pharmacokinetic (PK) profiles of SC and IV routes of administrations differ, SC administration has proven effective, safe, well-tolerated, and is generally preferred by patients and healthcare providers due to the greater flexibility and ease of administration for patients or their caregivers in their preferred setting (Gardulf 2007; Usmani 2021). In addition, SC administration has resulted in reduced drug delivery-related healthcare costs and resource utilization (Bittner 2018). In short, SC administration has become an attractive alternative to more invasive and time-consuming IV infusions.

Considering the GALAXI 1 results and the potential benefits of SC induction dosing to patients and healthcare systems, the aim of this study is to evaluate the efficacy, safety, and PK/pharmacodynamics (PD) profile of guselkumab SC induction compared with placebo in participants with moderately to severely active Crohn's disease.

2.2. Background

Nonclinical Studies

For the most current information on nonclinical development, refer to the guselkumab IB.

CONFIDENTIAL – FOIA Exemptions Apply in U.S.

Clinical Studies

The clinical development program for guselkumab includes studies in adult participants with psoriasis, psoriatic arthritis, palmoplantar pustulosis, rheumatoid arthritis, Crohn's disease, ulcerative colitis, familial adenomatous polyposis, hidradenitis suppurativa, lupus nephritis, and giant cell arteritis, as well as healthy participants. For a full list of completed and ongoing clinical studies, refer to the guselkumab IB.

Overall, through July 2021 (the data cutoff date for the guselkumab IB edition 12), an estimated 7,827 participants have been exposed to guselkumab across all indications in the clinical development program. As of July 2021, an estimated 703 healthy participants, 4,068 participants with psoriasis, 109 participants with rheumatoid arthritis, 1,509 participants with psoriatic arthritis, 182 participants with palmoplantar pustulosis, 472 participants with Crohn's disease, 175 participants with hidradenitis suppurativa, 540 participants with ulcerative colitis, 51 participants with familial adenomatous polyposis, 2 participants with giant cell arteritis, 7 participants with lupus nephritis, and 9 participants with systemic sclerosis have been exposed to guselkumab.

The overall clinical development program of guselkumab in participants with moderately to severely active Crohn's disease consists of the GALAXI program (CNTO1959CRD3001) and the CNTO1959CRD3004 SC induction study. The ongoing clinical program for guselkumab in Crohn's disease (CNTO1959CRD3001; GALAXI) is designed to evaluate the safety and efficacy of guselkumab compared with placebo and an active control (ustekinumab) in participants with moderately to severely active Crohn's disease, who have demonstrated an inadequate response or failure to tolerate previous conventional therapy or biologic therapy. The GALAXI program consists of 3 separate studies being conducted under a single protocol. GALAXI 1 was a 48-week Phase 2 dose-ranging study of the efficacy of guselkumab IV induction with doses of IV administered at Weeks 0, 4, and 8. GALAXI 2 and GALAXI 3 studies are 2 identical 48-week Phase 3 confirmatory studies. Participants who complete the 48-week Phase 2 or Phase 3 studies may be eligible to enter the long-term extension.

2.3. Benefit-risk Assessment

More detailed information about the known and expected benefits and risks of guselkumab may be found in the IB.

2.3.1. Risks for Study Participation

Potential Risks of Clinical Significance	Summary of Data/ Rationale for Risk	Mitigation Strategy
Clinical worsening of Crohn's disease	The benefit-risk of guselkumab for the treatment of moderately to severely active Crohn's disease has not been established.	 During the study, participants will be permitted to continue treatment of Crohn's disease with certain concomitant medications (Section 6.8). Participants will discontinue study intervention if it is not in their best interest or if they

Potential Risks of Clinical Significance	Summary of Data/ Rationale for Risk	Mitigation Strategy
		need to initiate protocol-prohibited medications including certain biologics (Sections 6.8 and 7.1). Participants in the placebo group who meet at least 1 of the rescue criteria will receive guselkumab (Section 6.5.1).
Risks	Due to Study Intervention Gusel	kumab
Serious infections and reactivation of latent infections	Available animal and human data suggest that blockade of IL-23 may be associated with an increased infection risk. Infections have been identified as adverse reactions of guselkumab, including respiratory infections, herpes simplex and tinea infections and gastroenteritis.	 Participants with a history of, or ongoing, chronic or recurrent infectious disease, including HIV, HBV or HCV, will be excluded from the study. Similarly, participants with evidence of active or untreated latent TB will be excluded from the study (Sections 5.1 and 5.2). Participants who have received a live viral or bacterial vaccination within 4 weeks prior to screening will be excluded from the study. In addition, participants must agree not to receive a live viral or live bacterial vaccination during the study and for 12 weeks after receiving the last dose of study intervention (Sections 5.2 and 5.3). Participants will be instructed to seek medical attention if they develop signs or symptoms suggestive of an infection, and investigators are instructed in the protocol to monitor for signs or symptoms of infections, including tuberculosis (Sections 8.2.9 and 8.2.10). Discontinuation of a participant's study intervention must be strongly considered if the participant develops a serious infection, including but not limited to sepsis or pneumonia. In addition, any serious infection should be discussed with the medical monitor or designee, and study

Potential Risks of Clinical Significance	Summary of Data/ Rationale for Risk	Mitigation Strategy
		intervention should be withheld until the clinical assessment is complete (Sections 7.1 and 8.2.9).
Hypersensitivity reactions, including serious hypersensitivity reactions	Serious hypersensitivity reactions including anaphylaxis have been reported in postmarketing experience with guselkumab in psoriasis patients.	 Participants with known allergy, hypersensitivity, or intolerance to guselkumab or its excipients will be excluded from the study (Section 5.2). Sites are instructed that before any administration of study intervention, appropriately trained personnel and medications (eg, injectable epinephrine) must be available to treat hypersensitivity reactions, including anaphylaxis. In addition, all participants must be observed carefully for signs and symptoms of a hypersensitivity reaction (eg, urticaria, itching, hives) (Section 8.2.8). Any participant who develops a serious hypersensitivity
		reaction such as anaphylaxis must discontinue study intervention (Section 7.1).
Malignancy	The preponderance of preclinical data suggests that blockade of endogenous IL-23 would not be detrimental and may in fact be beneficial in tumor immunosurveillance and host protection; however, a risk of malignancy cannot be excluded.	 Those participants who currently have a malignancy or have a history of malignancy within 5 years prior to screening (with exceptions noted in Section 5.2) will be excluded from the study. Additionally, participants who have a history of lymphoproliferative disease, including lymphoma; a history of monoclonal gammopathy of undetermined significance or signs and symptoms suggestive of possible lymphoproliferative disease, such as lymphadenopathy or splenomegaly will be excluded from the study (Section 5.2). During the conduct of the study, participants will undergo regular clinical monitoring including routine safety labs to assess for any changes in health

Potential Risks of Clinical Significance	Summary of Data/ Rationale for Risk	Mitigation Strategy
Liver injury	An SAE of 'toxic hepatitis' was reported in a participant in a Phase 2 Crohn's disease study who received guselkumab CI IV at Weeks 0, 4, and 8, and CI SC at Week 12. This event may represent drug-induced liver injury (DILI) possibly related to guselkumab (see Section 5.13.3 in the IB). Transaminase increases have been identified as an adverse reaction of guselkumab. In 2 Phase 3 psoriatic arthritis studies, increased ALT and/or AST was observed more frequently in patients treated with guselkumab CCI compared to patients treated with guselkumab CCI or placebo.	status that may indicate a possible malignancy. Participants who develop a malignancy during the study (with the exception of no more than 2 localized basal cell skin cancers that are treated with no evidence of recurrence or residual disease) will be discontinued from study intervention (Section 7.1). During the conduct of the study, liver function tests will be monitored at regular intervals in accordance with regulatory guidance (FDA 2009). In addition, the induction doses evaluated in this clinical program will not exceed CC Participants with marked liver enzyme elevations or symptoms or signs of liver dysfunction (eg, jaundice), should undergo a thorough investigation for possible causes of liver injury (Appendix 9, Section 10.9). A participant must have their study intervention discontinued if the participant has severe liver test abnormalities that are not transient and are not explained by other etiologies (Section 7.1).
Immunosuppression	It is unknown if guselkumab in combination with other immunosuppressives increases the risk of diseases associated with immunosuppression, such as infections or malignancy.	• In order to minimize the theoretical increased risk of infection or malignancy with the combination of guselkumab with immunosuppressive therapy, the baseline dose of oral corticosteroids on study entry is limited to ≤40 mg prednisone or its equivalent per day, or 9 mg/day of budesonide, or 5 mg/day beclomethasone, which must be tapered from Week 12 onwards. Furthermore, participants receiving AZA, 6-MP, or MTX, must have been taking them for ≥12 weeks and been on a stable dose for at

Potential Risks of Clinical Significance	Summary of Data/ Rationale for Risk	Mitigation Strategy
		least 4 weeks before the baseline visit. Additionally, participants are also excluded from the study if they have received cyclosporine, mycophenolate mofetil, tacrolimus, sirolimus, ustekinumab, or anti-TNFα therapy within 8 weeks, or vedolizumab within 12 weeks prior to the first dose of study intervention. Further detail regarding concomitant medications is provided in Sections 5.1 and 5.2. • During study participation, the use of immunomodulators other than AZA, 6-MP, and MTX (eg, cyclosporine) as well as biologic immunomodulators (eg, TNFα antagonists, vedolizumab) is prohibited. Participants initiating these treatments will be discontinued from further study intervention administration (see Section 6.8 for further details on prohibited concomitant medications).
	Risks Due to Study Procedure	
Risks associated with the	These risks are well-recognized,	Trained and experienced
endoscopy procedure including bleeding and colonic perforation	but are rare (Arora 2009; Rabeneck 2008).	endoscopists will be performing the procedure during this study.

Abbreviations: 6-MP=6-mercaptopurine; ALT=alanine transaminase; AST=aspartate transaminase; AZA=azathioprine; DILI=drug induced liver injury; FDA=Food and Drug Administration; HBV=hepatitis B virus; HCV=hepatitis C virus; HIV=human immunodeficiency virus; IB=Investigator's Brochure; IL=interleukin; IV=intravenously; MTX=methotrexate; q4w= every 4 weeks; q8w=every 8 weeks; SAE=serious adverse event; SC=subcutaneously; TB=tuberculosis; TNF=tumor necrosis factor alpha

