7.1. Discontinuation of Study Intervention

A participant who discontinues study intervention will not be automatically withdrawn from the study (see Section 7.2).

A participant's study intervention must be discontinued if:

- 1. The participant initiates treatment with prohibited therapies for Crohn's disease (Section 6.8).
- 2. The participant has a Crohn's disease-related surgery that represents a lack of efficacy of study intervention or that will preclude the future ability to assess efficacy using the CDAI or other instruments required for demonstration of efficacy endpoints.
 - Note: Other permitted Crohn's disease-related surgeries (eg, to resolve long-standing complications such as strictures or for symptomatic nonhealing fistulas, in participants experiencing improvement on study intervention) other than minor procedures (eg, placement of a seton or cutaneous drainage of an abscess) should be postponed until after the FES follow-up visit, unless necessary to ensure participant well-being and/or safety.
- 3. The participant becomes pregnant or plans a pregnancy within the study period (Section 8.3.5).
- 4. The participant (or the participant's representative) withdraws consent to receive study intervention.
- 5. The participant develops a systemic opportunistic infection.
- 6. The participant meets **ANY** of the following TB-related conditions:
 - A diagnosis of active TB is made.

- A participant has symptoms suggestive of active TB based on follow-up assessment questions and/or physical examination or has had recent close contact with a person with active TB and cannot or will not continue to undergo additional evaluation.
- A participant undergoing evaluation has a chest imaging with evidence of current active TB and/or a positive IGRA test result, unless active TB can be ruled out and appropriate treatment for latent TB can be initiated prior to the next administration of study intervention and continued to completion (see also Section 8.2.10). Indeterminate/borderline results should be handled as outlined in Section 8.2.10.
- A participant receiving treatment for latent TB discontinues this treatment prematurely or is noncompliant with the therapy.

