- 7. The participant has a serious adverse reaction that is related to an injection, including an injection-site reaction, resulting in bronchospasm with wheezing and/or dyspnea that requires ventilatory support **OR** that results in symptomatic hypotension with a decrease in systolic blood pressure >40 mmHg or blood pressure <90/60 mmHg.
- 8. The participant has a reaction resulting in myalgia and/or arthralgia with fever and/or rash (suggestive of serum sickness and not representative of signs and symptoms of other recognized clinical syndromes) occurring 1 to 14 days after an injection of study intervention. These may be accompanied by other events including pruritus, facial, hand, or lip edema, dysphagia, urticaria, sore throat, and/or headache.
- 9. The participant has a malignancy including squamous cell skin cancer. Consideration may be given to allowing participants who develop ≤2 basal cell skin cancers that are adequately treated with no evidence of residual disease to continue to receive study intervention.
- 10. The participant has severe liver test abnormalities that are not transient and are not explained by other etiologies, as described in Section 8.2.4 and Appendix 9 (Section 10.9).
- 11. The investigator believes that for safety reasons or tolerability reasons (eg, AE), it is in the best interest of the participant to discontinue study intervention.

Discontinuation of a participant's study intervention must be strongly considered under the following conditions:

- 12. Persistent inadequate response or worsening of Crohn's disease:
 - a. The participant has a CDAI score >220 and <70-point reduction from baseline CDAI at both Week 20 and Week 24.

OR

b. The participant experiences AEs consistent with clinically significant worsening of Crohn's disease at any time during the study.

These events must be evaluated by the investigator. A consultation with the study medical monitor may also be considered, at the investigator's discretion. Discontinuation of study intervention must be considered in participants with clinically significant worsening of Crohn's disease where continuation of the study intervention is not in the best interest of the participant.

13. The participant develops a serious infection, including but not limited to sepsis or pneumonia.

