8.2.8. Hypersensitivity Reactions

Before any administration of study intervention at the study site, appropriately trained personnel and medications must be available to treat hypersensitivity reactions, including anaphylaxis. All participants must be observed carefully for symptoms of a hypersensitivity reaction (eg, urticaria, itching, hives). If a mild or moderate hypersensitivity reaction is observed, acetaminophen, nonsteroidal anti-inflammatory drugs, and/or diphenhydramine may be administered.

In the case of a severe hypersensitivity reaction (eg, anaphylaxis), SC aqueous epinephrine, corticosteroids, respiratory assistance, and other proper resuscitative measures are essential and must be available at the study site where the injections are being administered.

Participants who experience serious adverse reactions related to an injection should be discontinued from further study intervention administrations (see Section 7.1).

Participants who experience reactions following an injection that result in bronchospasm with wheezing and/or dyspnea that requires ventilatory support, or symptomatic hypotension with a decrease in systolic blood pressure greater than 40 mmHg or blood pressure <90/60 mmHg will not be permitted to receive additional study intervention (see Section 7.1).

Participants who experience reactions suggestive of serum sickness (resulting in symptoms such as myalgia and/or arthralgia with fever and/or rash that are not representative of signs and symptoms of other recognized clinical syndromes) occurring 1 to 14 days after an injection of study intervention, should be discontinued from further study intervention administrations. Note that these symptoms may be accompanied by other events including pruritus, facial, hand, or lip edema, dysphagia, urticaria, sore throat, and/or headache (see Section 7.1).

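### Protocol Section 2.3.1 promises a mandatory stop after any serious hypersensitivity reaction and cites Section 7.1, but Section 7.1 has no such item and Section 8.2.8 words the rule differently

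*Protocol*

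**What the plan says.** Three places in the protocol govern study drug after a serious hypersensitivity reaction.

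- **Section 2.3.1, risk table, hypersensitivity row.** The mitigation column begins "Any participant who develops a serious hypersensitivity" and continues "reaction such as anaphylaxis must discontinue study intervention (Section 7.1"). Anaphylaxis is the example, no physiological threshold is attached, and Section 7.1 is named as the place where the rule stands.
- **Section 7.1.** Items 1 to 11 come under the stem "A participant's study intervention must be discontinued if". Item 7 reads "The participant has a serious adverse reaction that is related to an injection, including an injection-site reaction, resulting in bronchospasm"; this respiratory limb also names wheezing, dyspnea and a need for ventilatory support. Its alternative limb is a reaction "that results in symptomatic hypotension with a decrease in systolic blood pressure >40 mmHg or blood pressure <90/60 mmHg". Item 8 begins "The participant has a reaction resulting in myalgia and/or arthralgia with fever and/or rash" and covers a serum-sickness picture 1 to 14 days after an injection. Item 11 applies when the investigator believes, on safety or tolerability grounds, that stopping is in the participant's best interest. Item 15, in the separate list of conditions for which stopping is only to be strongly considered, covers severe injection-site reactions.
- **Section 8.2.8.** It says first: "Participants who experience serious adverse reactions related to an injection should be discontinued from further study intervention administrations". Next it repeats the ventilatory-support and blood-pressure criteria of item 7, this time without the word serious, and says that such participants may receive no more study drug. Last, it says that serum-sickness-like reactions should lead to discontinuation. All three statements refer back to Section 7.1.

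**The concern.** Sections 2.3.1 and 8.2.8 both send the reader to Section 7.1, so a site is likely to treat 7.1 as the working list. Someone who follows the reference from 2.3.1 does not find the rule that 2.3.1 describes. For serious hypersensitivity the specific items in 7.1 are narrower, because they add physiological consequences that the risk table does not require.

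A site working from 7.1 alone could continue dosing after a reaction that 2.3.1 says must end treatment, while a site that has read the risk table would stop. The mitigation is one of the measures behind the benefit-risk conclusion in Section 2.3.3, and the same table row records that serious hypersensitivity, including anaphylaxis, has been reported in postmarketing use. What is at stake is consistent handling of a recognised safety event across sites.

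**Working it through.** No arithmetic applies. The check sets the triggers and their force side by side.

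| Place | Trigger | Must be serious? | Physiological threshold | Force |
|---|---|---|---|---|
| 2.3.1 | Hypersensitivity reaction | Yes | None | Mandatory |
| 7.1 item 7 | Injection-related reaction | Yes | Ventilatory support or stated hypotension | Mandatory |
| 7.1 item 8 | Serum-sickness-like, days 1 to 14 | No | None | Mandatory |
| 7.1 item 11 | Safety or tolerability reason | No | None | Mandatory once the investigator judges it so |
| 7.1 item 15 | Injection-site reaction | No (must be severe) | None | Strongly considered |
| 8.2.8, first statement | Injection-related reaction | Yes | None | Should |
| 8.2.8, second statement | Reaction following an injection | No | As item 7 | No further drug permitted |
| 8.2.8, third statement | Serum-sickness-like, days 1 to 14 | No | None | Should |

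**Can a reaction be serious without meeting item 7?** Yes. The definition in Section 10.6.1 includes inpatient hospitalization and medically important events. Neither needs ventilatory support or hypotension.

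**Test case.** Take, as an illustration, a participant hospitalized with an anaphylactic reaction showing urticaria and angioedema, judged related to the injection, with no ventilatory support, no qualifying hypotension and no serum-sickness picture.

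1. Section 2.3.1: study drug must stop.
2. Section 8.2.8, first statement: study drug should stop. The second and third statements are not triggered.
3. Section 7.1: items 7 and 8 are not triggered, and item 15 does not describe a systemic reaction. Only item 11 is left, and it depends on what the investigator believes.

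The same participant meets three different rules.

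**Reverse case.** A reaction that meets the item 7 thresholds but is not classed as serious is barred from further drug by 8.2.8, yet falls outside item 7 as worded. This is a real difference in text but of little practical weight, since a reaction of that kind would usually be serious under Section 10.6.1.

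**Ambiguity inside item 7.** It is unclear whether the ventilatory-support condition applies to bronchospasm as well as to dyspnea. Neither reading removes the mismatch.

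**Are other rows of the risk table equally loose?** Two that were compared are not. The liver row follows 7.1 item 10, and the serious-infection row carries the same strongly-considered force as item 13.

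**The case against.** The strongest reply is that all three sections point towards stopping and none permits dosing to continue. Section 2.3.1 is protocol text, and Section 10.5.1 obliges the investigator to follow the protocol, so a site that reads the whole document stops the drug. Item 11 also stands in the mandatory list. On this view only a cross-reference has failed.

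Much of that is right, and it limits the point. A reader might infer that the protocol allows re-dosing after anaphylaxis, or that the stopping commitment does not exist. Neither follows, because the commitment is there in 2.3.1. What stands is that 2.3.1 is unconditional and cites a list that does not contain it, and that a clause resting on judgement is not the same rule.

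Four other stronger readings also fail.

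- *Every serious hypersensitivity reaction below the item 7 thresholds is left out of 7.1.* Item 8 requires stopping for serum-sickness-like reactions with no such threshold.
- *Section 7.1 is narrower throughout.* It is narrower only for serious hypersensitivity. Item 7 also reaches serious injection reactions that are not allergic, and item 8 does not require seriousness.
- *The change from must to should marks a deliberately weaker rule.* Section 8.2.8 also says should for the serum-sickness-like reactions that 7.1 item 8 makes mandatory, so the verb looks like drafting style and is weak evidence on its own.
- *Home injection makes the gap worse.* Section 6.1 does allow self-administration at home up to Week 244, but it also tells participants to contact the investigator promptly about signs of an allergic reaction. The place of injection does not change which stopping rule applies afterwards.

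**Conclusion.** The inconsistency is real and stands in current, unredacted text. For a serious hypersensitivity reaction that meets neither item 7 nor item 8, Sections 2.3.1, 8.2.8 and 7.1 give three different answers. It is a conflict between stated safety rules, so it goes beyond a typographical slip, but it is confined to that class of reaction.

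Its size cannot be calculated. The documents give no expected rate of such reactions, and the number is probably small. The conclusion assumes only that the reaction is judged related to the injection and that serious has the meaning given in Section 10.6.1.

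A reader might infer a threat to the co-primary results. Under SAP Section 5.3.2.1, a discontinuation for this reason falls in intercurrent event category 5 and counts as nonresponse, so uneven application of the rule before Week 12 could in principle change a participant's responder status. The documents show no such effect and give nothing from which to estimate one, so the point rests on the clarity of the safety rule alone.

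**What to change.** Reconcile Protocol Sections 2.3.1, 7.1 and 8.2.8. Section 7.1 should carry a single rule for serious hypersensitivity and injection-related reactions, with one trigger and one verb. It should say whether seriousness is required and whether any physiological threshold applies. Sections 2.3.1 and 8.2.8 should then refer to that rule without restating it in other terms. The sponsor's clinical team decides which criteria apply; this review takes no position on that.

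The cost is protocol wording in three places, which can go into the next amendment. No procedure, visit, data collection or analysis is added by the reconciliation itself.
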